#### 7.4. Data sources

Teratogen Information Services (MotherToBaby sites) provide referrals from pregnant women who call and who are interested in participating in the OTIS/MotherToBaby Pregnancy Registry. Healthcare providers are also informed that patients with Tdap exposure can be referred to the OTIS /MotherToBaby Pregnancy Registry. Active recruitment strategies are also used, e.g., direct mailings to healthcare providers, website, and professional meetings.

Enrollment in the OTIS/MotherToBaby Pregnancy Registry is voluntary and requires informed consent by the pregnant woman. The OTIS/MotherToBaby Research Center is responsible for verifying the participant selection criteria, enrolling each participant, and securing informed consent, providing all pregnancy and post-partum follow-up interviews and medical record review, recording and storage of all data, and subsequent data analysis and interpretation.

As part of the OTIS/MotherToBaby Pregnancy Registry protocol, data are collected using maternal interview(s), medical record review (obstetric, delivery hospital, pediatric, and vaccine provider, if applicable), and the pregnancy exposure diary (Table 3). The exposure diary is used as a supplemental source of information about medications, vaccines taken or received in pregnancy.

**Table 3 Timing of Cohort Enrollment, Interviews, Examinations, and Medical Records**

	Any Time In Pregnancy	20-22 Weeks' Gestation 	32-34 Weeks' Gestation 	0-6 Weeks Post-Delivery	0-2 Months Post-Delivery
Referral 	√				
Enrollment and Consent 	√				
Enrollment Interview 	√				
Interim Interview I		√			
Interim Interview II			√		
Pregnancy Outcome Interview and Request for Medical Records				√	
Medical Record Acquisition and Review					√

 Participants may enroll in the study any time during pregnancy.

 If participant is enrolled and Intake Interview is conducted after 18 weeks' gestation, only one interim interview is conducted during pregnancy at 32-34 weeks gestation.

 If participant is enrolled and Intake Interview is conducted at 30 weeks' gestation or after, no Interim Interview is collected.

Medication or vaccine exposures entered into the database are coded using the Slone Drug Dictionary. Data are recorded on hard copies of forms and these records are retained by OTIS/MotherToBaby at the Research Center. These forms are considered the primary data sources for studies and can be adapted to add new data elements. Data from these forms are extracted and entered into a customized OTIS/MotherToBaby study database located in the Research Center.

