9. comparison of proportion of NICU admissions for bronchopulmonary dysplasia occurring in pregnancies ending in live birth including twins or higher order multiples between the *Boostrix*-exposed cohort and the comparison cohort by calculating relative risks and associated 95% confidence intervals.

Initial analysis will be unadjusted. Adjusted analyses will be conducted where numbers of events permit, multivariable analyses will be conducted to adjust for possible confounders.

For the *Boostrix*-exposed cohort, follow-up time with respect to the primary and secondary outcomes will start on the date of *Boostrix* vaccination, and for the comparator cohort, follow-up time will start on the 1st day of the 27th week of gestation.

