## 7. RESEARCH METHODS

### 7.1. Study Design

This study is an observational cohort study of pregnancy and neonatal/early infancy safety outcomes in pregnant women in the OTIS/MotherToBaby Pregnancy Registry who received the *Boostrix* vaccine any time on or after the 1st day of the 27th week of pregnancy. The comparator cohort includes pregnant women who received no Tdap vaccine from the first day of LMP to the end of pregnancy. The incidence rates of

maternal and infant outcomes for pregnancies exposed to the *Boostrix* vaccine on or after the 1st day of the 27th week of pregnancy until the end of pregnancy will be compared to those observed in a comparator cohort unexposed to any Tdap vaccine during pregnancy. The target sample size for the study by the end of a four-year recruitment period is 3,000 participants: 1,500 pregnant women in the *Boostrix* vaccine exposure cohort and 1,500 pregnant women in the Tdap vaccine-unexposed comparator cohort.

The study will be conducted by OTIS/MotherToBaby Research Center located at the University of California San Diego. The registry relies on voluntary reporting of pregnancy and exposures by women and health care providers who contact the North American OTIS/MotherToBaby Pregnancy Studies, or the MotherToBaby network.

The study design is appropriate for the study objectives in that mothers are enrolled in the OTIS/MotherToBaby Registry before the outcome of pregnancy is known, direct measures of relative and absolute risk can be computed, and a range of adverse pregnancy outcomes can be evaluated.

The study design includes the identification of women with *Boostrix* vaccine exposure on or after the 1st day of the 27th week of pregnancy, and a comparison group without exposure to a Tdap vaccine from the first day of LMP to the end of pregnancy.

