### 7.2.1. Inclusion/exclusion criteria

All participants must meet the following criteria to be eligible for inclusion in the study:

- Reside in the US at the time of enrollment
- Enrolled in the OTIS/MotherToBaby Pregnancy Registry and currently pregnant at the time of enrollment on or after 08 March 2004
- Pregnancy ending in either livebirth or stillbirth
- Availability of medical records for that pregnancy including from obstetric provider, hospital of delivery and pediatric provider

The study sample will consist of approximately 600 participants in each cohort that have previously been enrolled in the OTIS/MotherToBaby Pregnancy Registry before the end of pregnancy, have completed their pregnancies with either a livebirth or stillbirth outcome, and have sufficient medical record and exposure data to meet the study objectives. An additional 1,800 participants (900 in each cohort) will be enrolled over four years; these participants will enroll before the end of pregnancy, have completed their pregnancies with either a livebirth or stillbirth outcome, and have sufficient medical record and exposure data to meet the study objectives.

- Selection for consideration for inclusion of the 600 pregnancies in each cohort from those previously enrolled in the OTIS/MotherToBaby Pregnancy Registry will be made solely on the following criteria irrespective of pregnancy outcome
  - Pregnancy continuing as of the 1st day of the 27th week of gestation
  - Availability of data on Tdap vaccination status on or after the 1st day of the 27th week of gestation
  - If vaccinated, data available to document Tdap vaccination brand
  - Availability of the required medical records from obstetric, hospital and pediatric providers
  - Selection starting with most recent year of enrollment until sample size is met

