#### Exclusion Criteria

- Women who have previously been included in this study with a prior pregnancy.

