#### Exclusion Criteria

- Women who have received a Tdap vaccine anytime during pregnancy.
- Women who have previously been included in this study with a prior pregnancy.

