### **7.2.2. Study conduct**

The study will be conducted by investigators at the University of California OTIS/MotherToBaby Research Center. The OTIS/MotherToBaby organization is a network of university and health department based telephone information centers serving pregnant women and health care providers throughout the US (Leen-Mitchell, 2000). These services receive spontaneous telephone inquiries from women who are pregnant or considering pregnancy as well as from health care providers about the safety or risk associated with environmental exposures in pregnancy, including medications and vaccines. Trained Teratogen Information Specialists at each site provide appropriate risk assessment and referral for all patient and health care provider callers free of charge. These services also provide a basis for collaborative research such as this study. Thus, individual Teratogen Information Services located throughout the US serve as a primary source of referrals not only for *Boostrix*-exposed pregnancies but also for similarly ascertained pregnant women with no exposure to Tdap vaccination during pregnancy.

Other methods of raising awareness about the study are meeting exhibits at professional practice meetings nationally, regionally, and locally, direct mail to health care providers, media, social media, and website. Awareness activities will also be directed to maternal-fetal medicine specialists, obstetricians, primary care physicians (PCP), and other specialists caring for pregnant patients.

The GSK package labeling for *Boostrix* in the US contains information about the pregnancy exposure registry and encourages healthcare providers to register patients by calling the toll-free study number.

In addition, the American Academy of Allergy, Asthma, and Immunology as the study collaborator through the Vaccines and Medications in Pregnancy Surveillance System (VAMPSS) will be asked to promote recruitment among colleagues. The existing toll-free number for North American callers currently being utilized by all OTIS/MotherToBaby Pregnancy Studies [contact]) will be promoted.

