### 7.4.1. Maternal Interviews

Below is a detailed description of each interview as conducted under the OTIS/MotherToBaby Pregnancy Registry protocol:

- Intake/Enrollment Interview:** A structured maternal intake telephone interview is conducted at enrollment by a trained Research Associate from the OTIS/MotherToBaby Research Center. This interview includes questions on the following: pregnancy history, including major congenital malformations, genetic disorders, number of live births, and multiple gestations; current health history; pre-pregnancy weight and height; socioeconomic and demographic information including maternal and paternal occupation, education and ethnicity; income category; current medication use, both prescription and over the counter; other environmental or occupational exposures, alcohol, tobacco, caffeine and illicit drug

use, vaccine exposure prior to and during pregnancy; current pregnancy complications including illnesses; family history of adverse pregnancy outcomes, including major congenital malformations and genetic disorders; names and addresses of health care providers; and vaccine use during pregnancy. To supplement future interviews and improve recall, participants are given a pregnancy exposure diary to record any additional exposures (medications, vaccinations, vitamins, etc.) or events as the pregnancy progresses. Each woman is also sent the informed consent document and the US Health Insurance Portability and Accountability Act (HIPAA) Authorization Addendum (when applicable) via electronic signature or paper, and a research HIPAA compliant obstetric medical record release form.

- **Interim Interviews I and II:** Telephone interviews are conducted at 20-22- and 32-34-weeks' gestation (if enrolled before the interview interval) by a trained Research Associate from the OTIS Research Center. Women who have enrolled prior to 18 weeks post-LMP will be interviewed by telephone at 20-22 weeks post-LMP, 32-34 weeks post-LMP and within 2 to 6 weeks after the expected due date. Women who have enrolled between 19 and 20 weeks post-LMP will be interviewed at 32-34 weeks post-LMP (See [Table 3](#)). These interviews are intended to update records of pregnancy exposures (medications, vaccinations, vitamins, etc.), results of prenatal tests, events of interest since last interview (including if the pregnancy has ended prior to the expected due date), and contact information.

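### Preeclampsia/eclampsia and PROM that began before registry enrolment count as outcomes, because onset is dated from week 27 or vaccination and never from enrolment

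*Protocol*

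**What the plan says.** - **Entry.** Table 3, footnote 1: "Participants may enroll in the study any time during pregnancy". Footnote 3 provides for intake at 30 weeks or later, so late entry is expected.
- **Eligibility.** Section 7.2.1 requires a woman to be "Enrolled in the OTIS/MotherToBaby Pregnancy Registry and currently pregnant at the time of enrollment on or after 08 March 2004". The only exclusion for the exposed cohort is "Women who have previously been included in this study with a prior pregnancy"; the comparator cohort adds "Women who have received a Tdap vaccine anytime during pregnancy". Neither cohort excludes a woman who already has a study outcome.
- **Start of follow-up.** Abstract, Data Analysis: "follow-up time with respect to the primary and secondary outcomes will start on the date of" vaccination in the exposed cohort. In the comparator cohort it starts on the first day of week 27.
- **Outcome windows.** Table 1 counts preeclampsia/eclampsia and PROM from week 27 or vaccination, whichever is later (PROM until 37 weeks). SGA is judged on size at birth. No definition uses the enrolment date.
- **Rationale.** Section 7.1 calls the design appropriate because "mothers are enrolled in the OTIS/MotherToBaby Registry before the outcome of pregnancy is known". Section 7.9 repeats this as a strength.
- **Late entry.** Section 7.7.1 recognises selection through late entry for preterm delivery only and uses survival methods there. The Abstract compares preeclampsia/eclampsia and PROM as proportions with relative risks.
- **Data already held.** The intake interview asks about "current pregnancy complications including illnesses" (Section 7.4.1), and obstetric records are obtained (Section 7.4.2).

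**The concern.** Enrolment before the outcome is known holds for events that end the pregnancy. It is not assured for preeclampsia, or for PROM followed by a latent period, because a woman can have either and still be pregnant and eligible. If the diagnosis affects whether she joins the registry, and does so differently in the two cohorts, the relative risk partly measures recruitment.

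Differential recruitment is plausible. The product label "encourages healthcare providers to register patients by calling the toll-free study number" (Section 7.2.2). The sponsor will encourage exposed women or their providers to make contact, and Section 7.4 says providers are told that patients with Tdap exposure can be referred. The preterm-delivery methods address the reverse problem, early events that never enter the study. For preeclampsia/eclampsia and PROM, events that precede entry are included. In a postmarketing safety study, a spurious excess or a masked one would be hard to untangle afterwards.

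**Working it through.** The plan gives no figure on this point: Table 4 has no row for preeclampsia or PROM, and no late-enrolment share is stated. The check is which cases count, and then how many would matter.

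**1. Which cases count (illustrative timings)**
- Vaccinated at 28 weeks, preeclampsia at 31, enrolled at 32: counts, although onset precedes enrolment.
- Unvaccinated, preeclampsia at 30 weeks, enrolled at 32: counts, although onset precedes enrolment.
- Preeclampsia before week 27, or before vaccination in the exposed cohort: does not count.
- Enrolled before the window opens: cannot contribute a pre-enrolment case.

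The gap is therefore the interval between the start of the window and enrolment, in either cohort.

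**2. How many net extra cases produce a significant excess when the true relative risk is 1**

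Inputs: n = 1,500 per cohort (Section 7.5); comparator rates of 1% and 2%, the top of the range that Section 7.5 expects for the other secondary endpoints. With a exposed and c comparator cases, the crude lower 95% limit is exp[ln(a/c) − 1.96·√(1/a − 1/n + 1/c − 1/n)].
- 1%: c = 15. At a = 27, exp(0.588 − 0.627) = 0.96. At a = 28, exp(0.624 − 0.623) = 1.001. **13 extra cases**, 13/1,500 = 0.9% of the cohort.
- 2%: c = 30. At a = 47, exp(0.449 − 0.452) = 0.997. At a = 48, exp(0.470 − 0.451) = 1.02. **18 extra cases**, 18/1,500 = 1.2%.

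**3. How strong the selection would have to be**

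All three selection inputs are assumptions: L = share of the exposed cohort enrolling late; f = share of cases already diagnosed at late enrolment; k = relative enrolment of such women, exposed versus comparator. With outcome rate p, the risk among late exposed enrollees is pL = [k·p·f + p(1−f)] / [k·p·f + p(1−f) + 1 − p], and the apparent relative risk is [(1−L)·p + L·pL]/p. At p = 2%:

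| L | f | k | Apparent RR | Chance of a significant excess |
|---|---|---|---|---|
| any | any | 1 | 1.00 | 2.5% |
| 0.10 | 0.25 | 2 | 1.02 | 3.1% |
| 0.25 | 0.50 | 2 | 1.12 | 6.7% |
| 0.50 | 0.50 | 3 | 1.48 | 39% |

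Last row: pL = (0.03 + 0.01)/(0.04 + 0.98) = 0.0392; (0.5 × 0.02 + 0.5 × 0.0392)/0.02 = 1.48. If the comparator were the over-selected cohort, the ratio would invert: 1/1.48 = 0.68.

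**4. Whether adjusting for time of enrolment helps**

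In the last row the relative risk is 1.00 among early enrollees and 0.0392/0.02 = 1.96 among late ones. Standardising to the exposed cohort's split returns 0.5 × 1.00 + 0.5 × 1.96 = 1.48. The bias lies within the late stratum, so adjustment for gestational age at enrolment leaves it in place.

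**5. SGA**

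At 10% of 1,425 (Table 4), 175 against 142 cases, 33 extra, puts the lower limit just above 1. Here f is the share of SGA pregnancies in which growth restriction was already suspected at late enrolment. The second and third rows of the table then give 1.02 (3.9%) and 1.11 (15%).

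**The case against.** - **No differential enrolment, no false signal.** This stands: with equal enrolment the ratio is 1.00. Section 7.2.2 also names the teratogen information services as a main referral source for comparators, so a comparator channel exists. What exposed women have in addition is the product-specific route.
- **No passage describes referral triggered by a current diagnosis.** Also true. The Section 7.9 example concerns vaccinated women with a prior preterm delivery, and that history is a listed confounder. The mechanism is plausible, not documented.
- **Partial handling exists.** Gestational age at enrolment and referral source are listed confounders (Table 2), but adjustment cannot remove a case that preceded entry, and it is planned only where event numbers permit. Choosing the 600 past registrants per cohort irrespective of outcome governs selection within the registry, not who joined it.
- **Detailed definitions are deferred to the SAP.** The protocol itself, however, fixes the windows and the start of follow-up.
- **Counting only post-enrolment events could hide harm.** This is right for a simple proportion. Late enrollees have less time at risk, and if exposed women enrol later, their risk is understated. Any restricted analysis needs delayed entry.

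A reader might infer that every diagnosis present at enrolment counts. It does not, because onset before week 27 or before vaccination is outside the window. A reader might also infer that known growth restriction is a prevalent outcome. It is not: SGA is measured at birth and always follows enrolment, so only selective enrolment remains.

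**Conclusion.** The point holds for preeclampsia/eclampsia and PROM. Cases with onset between the start of the outcome window and registry enrolment count, against the stated rationale, and neither the late-entry methods in Section 7.7.1 nor the sensitivity analyses in Section 7.7.2 cover them.

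A net 13 (at 1%) to 18 (at 2%) such cases among 1,500 exposed women would be enough for a nominally significant crude excess under a true relative risk of 1. These figures take the Section 7.5 rates at face value. Whether that many would arise rests on L, f and k, which the protocol does not give; mild settings move the ratio only to 1.02. A reader might infer that the results will be biased against the vaccine. The documents do not support that, since the bias may run either way or be absent.

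This should be fixed but is not critical. The two outcomes directly affected are secondary with admittedly limited power, and the SGA issue needs only a sensitivity analysis.

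**What to change.** In Sections 7.7.1 and 7.7.2:
1. Tabulate, by cohort, preeclampsia/eclampsia and PROM cases with onset before registry enrolment.
2. Pre-specify for each of these outcomes an analysis of women free of the condition at the latest of week 27, vaccination and enrolment. Count only later onset and use delayed entry, as already planned for preterm delivery, so that shorter time at risk in late enrollees does not bias the comparison.
3. For SGA, add a sensitivity analysis excluding pregnancies with growth restriction recorded before enrolment.
4. Qualify the statements in Sections 7.1 and 7.9 that women enrol before the outcome is known.

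The cost is mainly wording. The intake interview and obstetric records already supply the information, and Table 1 already requires the timing of onset. Some events and late-enrolled women drop out of the added analyses, with slightly wider intervals for outcomes that are already sparse.

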### 7.4.1. Maternal Interviews

Below is a detailed description of each interview as conducted under the OTIS/MotherToBaby Pregnancy Registry protocol:

- Intake/Enrollment Interview:** A structured maternal intake telephone interview is conducted at enrollment by a trained Research Associate from the OTIS/MotherToBaby Research Center. This interview includes questions on the following: pregnancy history, including major congenital malformations, genetic disorders, number of live births, and multiple gestations; current health history; pre-pregnancy weight and height; socioeconomic and demographic information including maternal and paternal occupation, education and ethnicity; income category; current medication use, both prescription and over the counter; other environmental or occupational exposures, alcohol, tobacco, caffeine and illicit drug

use, vaccine exposure prior to and during pregnancy; current pregnancy complications including illnesses; family history of adverse pregnancy outcomes, including major congenital malformations and genetic disorders; names and addresses of health care providers; and vaccine use during pregnancy. To supplement future interviews and improve recall, participants are given a pregnancy exposure diary to record any additional exposures (medications, vaccinations, vitamins, etc.) or events as the pregnancy progresses. Each woman is also sent the informed consent document and the US Health Insurance Portability and Accountability Act (HIPAA) Authorization Addendum (when applicable) via electronic signature or paper, and a research HIPAA compliant obstetric medical record release form.

- **Interim Interviews I and II:** Telephone interviews are conducted at 20-22- and 32-34-weeks' gestation (if enrolled before the interview interval) by a trained Research Associate from the OTIS Research Center. Women who have enrolled prior to 18 weeks post-LMP will be interviewed by telephone at 20-22 weeks post-LMP, 32-34 weeks post-LMP and within 2 to 6 weeks after the expected due date. Women who have enrolled between 19 and 20 weeks post-LMP will be interviewed at 32-34 weeks post-LMP (See [Table 3](#)). These interviews are intended to update records of pregnancy exposures (medications, vaccinations, vitamins, etc.), results of prenatal tests, events of interest since last interview (including if the pregnancy has ended prior to the expected due date), and contact information.
- **Pregnancy Outcome Interview:** A structured telephone interview is conducted by a trained Research Associate from the OTIS Research Center at 0 to 6 weeks after the expected due date, or at an interim interview point or earliest convenient time for the participant if pregnancy has ended. This interview elicits information based on type of birth:
  - For women with live born infants: date of delivery, hospital location and mode of delivery; sex, birth weight, length and head circumference; Apgar scores; description of delivery or birth complications including preeclampsia/eclampsia, premature rupture of the membranes, malformations; type and length of hospital stay for pregnant women and their infants; survival of the infant to 28 days of life; delivering physician's and infant physician's names and addresses; method of infant feeding; pregnancy weight gain; and additional exposures, results of prenatal tests occurring since the previous interview, and additional study-related outcomes for mothers and infants including neonatal sepsis and bronchopulmonary dysplasia.
  - For women with stillborn infants: date and type of outcome; hospital location if applicable; prenatal diagnosis; pathology results if available; and additional exposures and results of prenatal tests occurring since the previous interview, sex of the infant, delivery or birth complications including preeclampsia/eclampsia and premature rupture of the membranes, malformations, birth size and autopsy results if available.

